7. SELECTION AND WITHDRAWAL OF SUBJECTS

7.1. Subject Inclusion Criteria

- 1. Pediatric patients 2-17 years of age and weighing ≥ 10 kg.
- Patients requiring a sum norepinephrine-equivalent dose of > 0.1 μg/kg/min (see Appendix B for conversion) for a minimum of 2 hours and a maximum of 48 hours prior to initiation of LJPC-501 dosing.
- 3. Patients must have a clinical diagnosis of distributive shock in the opinion of the treating team and the Investigator.
- 4. Patients are required to have central venous access, which is expected to remain present for the duration of LJPC-501 treatment.
- 5. Patients are required to have an indwelling arterial line, which is expected to remain present for at least the first 24 hours of LJPC-501 treatment.
- 6. Patients must have received at least 40 mL/kg of crystalloid or colloid equivalent over the initial 24-hour resuscitation period, and are adequately volume resuscitated in the opinion of the Investigator.
- 7. Patient should receive VTE prophylaxis per institutional guidelines, if indicated, before beginning treatment with LJPC-501.
- 8. Parent or legal guardian is willing and able to provide informed consent and assist the patient in complying with all protocol requirements.

7.2. Subject Exclusion Criteria

- 1. Patients who are < 2 years of age or ≥ 18 years of age.
- 2. Patients who weigh < 10 kg.
- 3. Patients with a standing Do Not Resuscitate order.
- 4. Patients diagnosed with acute occlusive coronary syndrome requiring pending intervention.
- 5. Patients on veno-arterial (VA) extracorporeal membrane oxygenation (ECMO).
- 6. Patients who have been on veno-venous (VV) ECMO for less than 6 hours.
- 7. Patients with a clinical suspicion of cardiogenic shock
- 8. Patients who have a history of asthma or are currently experiencing bronchospasm requiring the use of inhaled bronchodilators and who are not mechanically ventilated.
- 9. Patients with acute mesenteric ischemia or a history of mesenteric ischemia.
- 10. Patients with active bleeding AND an anticipated need of multiple transfusions (within 48 hours of Screening).

- 11. Patients with active bleeding AND hemoglobin < 7 g/dL or any other condition that would contraindicate serial blood sampling.
- 12. Patients requiring more than 5 mg/kg daily of hydrocortisone or equivalent glucocorticoid medication as a standing dose.
- 13. Patients with an expected lifespan of < 12 hours or withdrawal of life support within 24 hours of Screening.
- 14. Patients with a known allergy to mannitol.
- 15. Patients who are currently receiving an investigational drug (active or placebo) as part of another clinical trial.
- 16. Patients of childbearing potential who are known to be pregnant at the time of Screening.

7.3. Subject Withdrawal Criteria

Patients and their parent(s) or legal guardian(s) will be informed that they have the right to withdraw from the study at any time and for any reason, without prejudice to their medical care. The Investigator also has the right to withdraw patients from the study for any of the following reasons:

- Clinically significant concurrent illness
- Occurrence of an unacceptable AE
- Request of patient, parent(s), or legal guardian(s)
- Major protocol violations
- Non-compliance
- Administrative reasons
- General or specific changes in the patient's condition unacceptable for further treatment based upon the judgment of the Investigator

At the time of withdrawal, all study procedures for EOS are to be completed, if possible. The reason(s) for a patient's withdrawal from the study are to be recorded on the appropriate case report form (CRF).

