A schedule of study procedures is shown in Table 4. Patients will be monitored for hemodynamic vital signs (MAP, HR) at Screening and at approximately -15, -5 and 0 minutes (or just prior to initiation of LJPC-501 dosing) to establish the Baseline MAP value. MAP should be assessed once every 5 minutes during the first 15 minutes of LJPC-501 treatment, then once every 15 minutes up to the Hour 2 time point and at least once hourly thereafter through the duration of LJPC-501 administration (at minimum 24 hours). Additionally, MAP should be assessed just prior to every dose titration. If LJPC-501 administration is continued for longer than 24 hours, MAP should be assessed hourly and just prior to any dose adjustment until LJPC-501 is discontinued.

[figure not shown]
Treatment with LJPC-501 will continue to Hour 24, with the goal of maintaining age-, size-, and disease-appropriate MAP (Appendix A, Dellinger 2013), while reducing the reliance on SOC vasopressors. Down-titration of SOC vasopressors should be done according to individual institutional protocols and the Investigator's discretion.

After 24 hours, LJPC-501 treatment may be stopped or continued up to 7 days (168 hours) at the Investigator's discretion. It is recommended that the Investigator check in with the Sponsor's contact to continue treatment for more than 24 hours. If the Investigator determines that it is necessary to discontinue LJPC-501 prior to Hour 24, the Sponsor should also be consulted prior to discontinuation. To stop treatment, LJPC-501 will be titrated off by decreasing the dose at the Investigator's discretion and according to guidelines in Section 8.3.2. After Hour 24, if LJPC-501 treatment has been stopped for 3 hours or less, the Investigator may reinitiate treatment after consultation with Sponsor; if treatment has been stopped for more than 3 hours it may not be reinitiated. All patients will be followed for a minimum of 7 days, or for 72 hours (3 days) \pm 6 hours following discontinuation of LJPC-501, whichever is later, before end-of-study (EOS) assessments.

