6.6.1. Safety Criteria for Adjustment or Stopping Doses

LJPC-501 administration may continue through Day 7 to support an age- and disease-appropriate MAP. At any time during dosing, if clinically significant toxicities or worsening of symptoms of underlying disease is observed, treatment should be down-titrated and discontinued.

LJPC-501 infusion should not be stopped abruptly (see dose titration guidelines in Section 8.3.2). To discontinue, down titrate by 5 to 20 ng/kg/min every 15 minutes until a dose of 10 ng/kg/min is reached. After 15 minutes at 10 ng/kg/min, down titrate to 5 ng/kg/min. After 15 minutes at 5 ng/kg/min down titrate to 2.5 ng/kg/min. Discontinue LJPC-501 infusion after 15 minutes at 2.5 ng/kg/min.

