² Patients will be followed for a minimum of 7 days, or for 72 hours (3 days) ± 6 hours following discontinuation of LJPC-501, whichever is later, before end of study (EOS) assessments are completed. Depending on the duration of treatment, EOS may occur on Day 7 through Day 10. If a patient is treated for the target minimum of 24 hours, EOS will occur on Day 7.

³ Informed consent must be obtained before any study related activities can occur. SOC procedures conducted prior to informed consent may be used to qualify patients for the study, if performed within the specified time window for the procedure (Section 8.5).

⁴ All patients will have their SOC vasopressors titrated (to a total sum NE equivalent dose of > 0.1 μg/kg/min to be eligible) for a minimum of 2 hours but not for longer than 48 hours prior to initiation of LJPC-501 dosing. During the first two hours of LJPC-501 treatment, SOC vasopressor dosing may be decreased, but not increased, unless adjustment is required for safety reasons. After Hour 2 and throughout LJPC-501 treatment, up to Day 7, titration of SOC vasopressors may continue with the goal of sparing the use of catecholamines. (X) indicates time periods during which LJPC-501 dose administration is optional. During treatment with LJPC-501, SOC vasopressor titration should be tracked.

⁵ Do not continue administration for more than 7 days (168 hours).

⁶ A limited physical exam (PE) focused on extremities, abdominal region and neurological system should be performed at Screening and at EOS. Screening PE will also document body weight and height.

⁷ Chest X-ray is optional. SOC chest X-rays collected prior to informed consent but within 24 hours prior to LJPC-501 treatment initiation may be used.

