11.2.4. Reporting of Adverse Events and Serious Adverse Events

11.2.4.1. Reporting of Adverse Events

All AEs will be recorded from initiation of study drug treatment, during treatment, and through EOS, regardless of the causal relationship to the investigational product.

All AEs, whether believed by the Investigator to be related or unrelated to the investigational product, must be documented in the patient's medical records/source documents, in accordance with the Investigator's normal clinical practice and on the AE CRF. Each AE is to be evaluated for duration, intensity, frequency, seriousness, outcome, other actions taken, and relationship to the investigational product.

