11.2.4.2. Reporting of Serious Adverse Events

In agreeing to the provisions of this protocol, the Investigator accepts all legal responsibilities for immediately reporting of SAEs to La Jolla. Immediate reporting implies within 24 hours of becoming aware of the occurrence of a SAE.

All SAEs that occur from initiation of study drug treatment, during treatment, and through the Day 28 follow-up, regardless of the causal relationship to the investigational product, must be reported to La Jolla by following the instructions provided in this Section. Redacted medical record source documentation will be requested for all SAEs and emergency room visits.

The method for reporting a SAE is by completing and sending the Serious Adverse Event Report Form and completing the AE CRF. The Serious Adverse Event Report Form and if applicable, a copy of redacted source documents (such as hospital discharge summary, medical records, etc.) related to the SAE will be sent as:

- e-mail to: [contact]; or
- fax to: [contact]

The Investigator will assess whether the event is causally related to the investigational product. La Jolla will also assess whether the event is causally related to the investigational product, in addition to assessing the overall safety profile of the investigational product. La Jolla will notify the appropriate regulatory authorities in accordance with country regulations. It is the Investigator's responsibility to notify the IRB or independent ethics committee (IEC) of all SAEs that occur at his or her site, according to local requirements. Investigators will be informed about SAEs according to applicable local regulations. Each site is responsible for notifying its IRB/IEC of these additional SAEs, per local policy.

Following the initial report, any additional information obtained by the Investigator about the SAE must be reported promptly to La Jolla in the same manner as described above for the initial SAE report.

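### Section 7.3 places EOS at investigator withdrawal, against Day 7 or later in Section 6.2; a site that takes the withdrawal visit as EOS would stop recording new non-serious AEs early in children withdrawn for toxicity or worsening

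*Protocol*

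**What the plan says.** **Leaving the study.** Section 7.3 states: "The Investigator also has the right to withdraw patients from the study for any of the following reasons". The list includes clinically significant concurrent illness, an unacceptable AE, and a change in the patient's condition that is "unacceptable for further treatment based upon the judgment of the Investigator". The last is a reason to stop treatment that is used here as a reason to leave the study. The section continues: "At the time of withdrawal, all study procedures for EOS are to be completed, if possible". It says nothing about follow-up after that.

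**When EOS falls.** Section 6.2 states: "All patients will be followed for a minimum of 7 days, or for 72 hours (3 days", with a 6-hour allowance, counted from the stop of LJPC-501. Table 4 footnote 2 repeats the rule: "following discontinuation of LJPC-501, whichever is later, before end of study (EOS) assessments are completed". It gives the resulting range as Day 7 to Day 10. Neither place makes an exception for withdrawn patients.

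**Stopping drug.** Section 6.6.1 deals with much the same events at the level of treatment only: "if clinically significant toxicities or worsening of symptoms of underlying disease is observed, treatment should be down-titrated and discontinued".

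**What EOS ends.** Section 11.2.4.1 states: "All AEs will be recorded from initiation of study drug treatment, during treatment, and through EOS". Section 11.2.4.2 has the longer window: "All SAEs that occur from initiation of study drug treatment, during treatment, and through the Day 28 follow-up". Section 8.5.11 limits the Day 28 contact to SAEs, apart from medications and procedures. Section 11.2.5 keeps following AEs that are still open at the last visit if they are related or otherwise clinically significant.

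**The concern.** The same clinical event can lead to either of two EOS times. Under Section 6.6.1 the patient stops drug and stays under the Section 6.2 rule. Under Section 7.3 the patient leaves the study and has EOS procedures at once. Because EOS also closes the recording of non-serious AEs, the choice of section can set how long a child is observed for them.

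The shortened records would belong to children withdrawn for toxicity or deterioration, so the loss would be related to outcome. Safety and tolerability is the first secondary objective (Section 5.3). The study has one arm and 10 to 30 patients, and Section 4.6 says that the risk of adverse events in children is unknown. An AE summary that loses time in these patients leans towards fewer events, with no control arm losing time in the same way. This cannot be left to the analysis plan, because no analysis recovers events that were never recorded.

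**Working it through.** **Inputs**
- Planned EOS: the later of 7 days (168 h) and 72 h after LJPC-501 stops, with a 6-hour allowance (Section 6.2; Table 4 footnote 2).
- Longest treatment: 168 h (Table 4 footnote 5).
- EOS procedures in a withdrawn patient: at withdrawal (Section 7.3).
- Recording of non-serious AEs: from start of drug through EOS (Section 11.2.4.1).

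**Formulae.** Let D be the hour at which drug stops and W the hour of study withdrawal.
- Planned EOS = max(168, D + 72).
- Recording lost = planned EOS − W, if the site takes the withdrawal visit as EOS.

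**The plan's own figure.** For D up to 96 h, D + 72 is at most 168, so EOS is at 168 h, which is Day 7. For D = 168 h, EOS is at 168 + 72 = 240 h, which is Day 10. This reproduces the Day 7 to Day 10 range in footnote 2.

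**Drug stops at withdrawal (D = W = t).** The loss becomes max(168 − t, 72).

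| t (h) | Planned EOS (h) | Lost (h) | Share of window recorded |
|---|---|---|---|
| 24 | 168 | 168 − 24 = 144 | 24/168 = 14.3% |
| 48 | 168 | 168 − 48 = 120 | 48/168 = 28.6% |
| 72 | 168 | 168 − 72 = 96 | 72/168 = 42.9% |
| 96 | 168 | 168 − 96 = 72 | 96/168 = 57.1% |
| 120 | 192 | 192 − 120 = 72 | 120/192 = 62.5% |
| 144 | 216 | 216 − 144 = 72 | 144/216 = 66.7% |

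In this case the loss is never below 72 h. Using the allowance on the 72 h, it is never below 72 − 6 = 66 h.

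**Drug stopped before withdrawal.** With D = 24, planned EOS is 168 h. Withdrawal at 120 h then loses 168 − 120 = 48 h, and at 144 h it loses 24 h. The 72-hour floor therefore depends on drug and study participation ending together.

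**Does anything later restore the lost AEs?**
- Table 4 marks the AE/SAE row at Day 28. However, footnote 22 describes that contact as a check for reportable events after EOS. Under Sections 11.2.4.1 and 11.2.4.2, only SAEs are reportable by then, and Section 8.5.11 names only SAEs.
- Section 11.2.5 covers AEs that are already open, not new ones.
- What can be lost is therefore new non-serious AEs that start between withdrawal and the planned EOS.

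**The case against.** The strongest reply is that a general follow-up rule with an early-exit clause is a common structure. Section 7.3 permits withdrawal and does not require it, while Section 6.6.1 is the directive rule for toxicity and keeps the patient in the study. Section 7.3 also moves EOS procedures without saying that AE recording ends, and Section 6.2 speaks of all patients. This stands in part: the loss arises only where a site takes the withdrawal visit as EOS. But if Section 6.2 still governs withdrawn patients, the protocol gives them two EOS times and does not say which one closes AE recording.

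A second reply is that little is at stake. The AE that led to withdrawal began earlier and is recorded. SAEs run to Day 28 under a broad definition that includes prolonged hospital stay, and medications and procedures are recorded to Day 28. Drug would usually be off, and Section 4.4 reports a half-life below 60 seconds in rats. All of this stands and limits the point to new non-serious AEs.

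Stronger readings are tempting, but the documents do not support them:
- **At least 72 hours lost in every withdrawn patient.** This fails if drug stopped earlier. It also fails if the patient dies before the planned EOS, which matters in a deteriorating group.
- **A number of affected children derived from the 14% in Section 4.5.** That figure is treatment discontinuation for an AE in adults, which Section 6.6.1 handles here without study withdrawal. The protocol gives no basis for the share that would go through Section 7.3.
- **Loss of SAEs or of 28-day mortality.** Section 11.2.4.2 makes no exception for withdrawn patients. Vital status would be lost only if a site took withdrawal as cancelling the Day 28 contact, and the text does not say so.

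**Conclusion.** The point holds in a limited form. Sections 7.3 and 6.2 (with Table 4 footnote 2) give two EOS times for a patient whom the investigator withdraws for a clinical reason. Because Section 11.2.4.1 ties AE recording to EOS, following Section 7.3 can end the recording of new non-serious AEs early and selectively.

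Per affected patient, the loss is max(168 − t, 72) h. This assumes that the site takes the withdrawal visit as EOS, that drug stops at withdrawal, and that the patient would have survived to the planned EOS. How many patients this would touch is unknown and may be none.

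SAEs through Day 28, the AE that triggered withdrawal, and ongoing AEs that are related or clinically significant remain covered, and the Hour 2 endpoint does not depend on where EOS falls. This is a modest weakness in safety collection with a cheap repair, and it does not threaten the primary result.

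**What to change.** Leave the criteria for stopping treatment as they are. Reconcile Section 7.3 with Section 6.2, Table 4 footnote 2 and Section 11.2.4.1 by adding to Section 7.3:

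*A patient withdrawn by the Investigator for an AE, concurrent illness or change in condition, without withdrawal of consent for follow-up, remains in follow-up: AE recording continues to the EOS time set in Section 6.2 and SAEs are collected to Day 28, by chart review where assessment in person is not possible. EOS procedures are completed at the time of withdrawal when consent for follow-up is withdrawn, or when withdrawal is for protocol violation, non-compliance or administrative reasons.*

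The second sentence keeps an EOS rule for the non-clinical grounds, which would otherwise have none. No new visit is needed: daily AE assessment on Days 2 to 6 applies whether or not drug is given (Sections 8.5.6 and 8.5.7), and the EOS and Day 28 contacts are already planned. The cost is a few more chart reviews, and some EOS examinations missed in patients who have left the unit.

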8. TREATMENT OF SUBJECTS

8.1. Description of Study Drug

LJPC-501 drug product is a sterile, aqueous solution for dilution prior to infusion that is supplied in single-dose vials (Table 5). Vials contain 2.5 mg/mL angiotensin II and 25 mg/mL mannitol as an excipient in water for injection. LJPC-501 is diluted in normal saline for continuous IV infusion administration. The infusion rate of LJPC-501 may be adjusted to maintain adequate MAP.

	Investigational Product
Product Name:	LJPC-501 (angiotensin II)
Dosage Form:	Injection
Unit Dose:	2.5 mg/mL
Route of Administration:	IV infusion
Physical Description:	aqueous solution
Manufacturer:	Emergent BioSolutions, Inc. (EBSI)

Table 5:Investigational Product

8.2. Concomitant Medications and Procedures

All patients should be given maximal supportive therapy during the course of the study. All medications and supportive therapies (including renal replacement therapy and ventilation support) that are administered from Screening through the Day 28 follow-up, including the dose and indication, must be recorded on the appropriate CRF and in the source documents. Supportive therapy that is ongoing at baseline will be permitted during the treatment phase of the study. No other experimental therapy is permitted. Concomitant medications for other medical conditions are permitted as clinically indicated. Concomitant procedures, such as dialysis, mechanical ventilation, and relevant procedures used to diagnose or treat a serious adverse event (SAE), will also be recorded from screening through Day 28.

Start and stop date(s)/time(s), dose, and amount administered will be recorded for vasopressors administered up to 48 hours prior to, during, and after LJPC-501 administration. Total daily dose for each vasopressor administered through Day 28 may be recorded after completion of LJPC-501 administration.

8.3. Titration of Standard-of-Care Vasopressors and LJPC-501

8.3.1. Titration of Standard-of-Care Vasopressors

During the Screening and baseline time periods, patients will have their SOC vasopressors titrated to an age-, size-, and disease-appropriate MAP (Appendix A, Dellinger 2013), per Investigator discretion. All patients will have their SOC vasopressors titrated (to a sum NED of $> 0.1 \mu g/kg/min$ to be eligible) for a minimum of 2 hours but not for longer than 48 hours prior to initiation of LJPC-501 dosing. The Screening MAP is defined as the average of at least 2 once-hourly MAP measurements collected during SOC vasopressor titration (when NED is $> 0.1 \mu g/kg/min$), and within 24 hours prior to LJPC-501 treatment initiation.

During the first two hours of LJPC-501 treatment, SOC vasopressor dosing may be decreased, but not increased, unless adjustment is required for safety reasons. After Hour 2 and throughout LJPC-501 treatment, titration of SOC vasopressors may continue with the goal of sparing catecholamine and other vasopressor use.

Baseline MAP will be assessed by 3 measurements documented within 15 minutes prior to initiation of LJPC-501 (ie, approximately -15 minutes, -5 minutes, and 0 minutes [just prior to initiation of study drug administration]). Standard-of-care vasopressor doses should not be changed during measurement of baseline MAP. Baseline NED is the NED at the time of initiation of LJPC-501.

8.3.2. Titration of LJPC-501

LJPC-501 infusion will be started at 5 ng/kg/min. After 5 minutes, the LJPC-501 infusion rate (dose) may be increased to increase MAP and/or allow reduction in SOC vasopressor doses. The dose of LJPC-501 may be increased by 5 ng/kg/min as frequently as every 5 minutes up to a maximum of 40 ng/kg/min. Any decision to increase the dose rate above 40 ng/kg/min must be made in consultation with Sponsor. With Sponsor approval, the dose rate may be increased to > 40 ng/kg/min (to a maximum of 80 ng/kg/min) by increases of 5 to 10 ng/kg/min as frequently as every 5 minutes.

Some patients may be more sensitive to the pressor effects of angiotensin II, and the LJPC-501 dose may be decreased to 1.25 ng/kg/min to avoid hypertension. If MAP exceeds 90 mmHg, SOC vasopressors should be down-titrated first, then LJPC-501 should be down-titrated if MAP remains \geq 90 mmHg.

LJPC-501 treatment should continue for at least 24 hours. Between Hour 2 and Hour 24, LJPC-501 may be titrated between 1.25 and 40 ng/kg/min (or up to 80 ng/kg/min with Sponsor approval). Treatment with LJPC-501 may continue up to 7 days (168 hours) with Sponsor approval.

Changes in LJPC-501 and SOC vasopressor doses should be avoided during MAP measurement at Hour 2 (for evaluation of primary endpoint) and at Hour 24 (for evaluation of secondary endpoint). Interruptions of LJPC-501 administration for longer than 5 minutes before Hour 24 should be avoided, unless required for patient safety, because they may interfere with efficacy assessments. For patients who have received LJPC-501 for the target 24-hour treatment period, treatment may be reinitiated if LJPC-501 treatment has been stopped for 3 hours or less; if treatment has been stopped for more than 3 hours it may not be reinitiated.

33 La Jolla Pharmaceutical Company - Confidential 19 March 2018 (Version 2.0) LJPC-501 infusion should not be stopped abruptly. To discontinue LJPC-501, down titrate by 5 to 20 ng/kg/min every 15 minutes until a dose of 10 ng/kg/min is reached. After 15 minutes at 10 ng/kg/min, down titrate to 5 ng/kg/min. After 15 minutes at 5 ng/kg/min down titrate to 2.5 ng/kg/min. Discontinue the LJPC-501 infusion after 15 minutes at 2.5 ng/kg/min.

